### ***Evaluation of sample size***

It is expected that out of 798 patients randomized 712 patients will complete the study per protocol. Taking into consideration the expected screening failures, the informed consent should be obtained from 838 patients.

The sample size was assessed on the basis of the following rules and assumptions:

1. Statistical provisions.
  - 1.1 the power of the statistical tests “ $P = (1 - \beta)$ ” is assumed to be 80% (the probability of correct rejection of the null hypothesis is 0.8);
  - 1.2 the probability of a type I error “ $\alpha$ ” is allowed to be less than 5% (the probability of false acceptance of an alternative hypothesis is less than 0.05);
  - 1.3 the study **does not plan** unblinded interim analysis;

---

 If, considering the lack of some data in primary endpoint variable, the fact of reaching the primary endpoint by the patient can still be determined, the patient will be eligible for PP analysis (e.g. the diary lacks some records but the time of recovery can still be determined).

 No more than 5% patients who signed PIS and ICF are expected to be screening failures for various reasons.

- 1.4 the applied statistical tests for group comparisons are two-sided, unless stated otherwise;
- 1.5 the sample size is calculated based on the assumptions on the expected effect declared in the primary endpoint of this protocol;
- 1.6 the ratio between the sample sizes of the study drug and placebo groups is 1:1 (1 study drug patient - 1 placebo patient);
- 1.7 statistical hypotheses: null and alternative hypotheses about the superiority of the study drug over placebo using the applied dosing regimen:

**primary endpoint:**

$$H_0: OR_{12} = 1$$

$$H_a: OR_{12} \neq 1$$

where : OR12 – is odds ratio for an event occurrence in Raphamin and Placebo groups (the lower, the better).

The following SAS program code was used to determine the required sample size:

*SAS code performed:*

```
proc power;  
twosamplefreq test=lrchi  
OR=0.5  
refp=0.15  
power=.8  
alpha=.04  
npergroup=.;  
run;
```

- 1.8 Full sample size is determined using the formula:

$$N = N_{pp} / (1 - R_w),$$

where N – the final sample size;

**Npp** – result of calculation in cl. 1.7, i.e. scheduled number of the patients completing the study per protocol;

**Rw** – withdrawal rate.

2. Assumptions on expected effects of the clinical study: Odds ratio for the event occurrence in Raphamin and Placebo groups is expected to be no more than **0.5** at population event frequency of at least **0.15** [32-34].

---

 The analysis stipulates for obligatory assessment and accounting for effects of additional factors: history of vaccination and age/age groups of the subjects.

 In assumption of reduced proportion of severe form in case of strain change (to Omicron) and based on the following sources:

Therefore, the number needed to compare study drug and placebo will be **712** patients for both groups. Given potential withdrawal of at least 15% patients (**Rw = 0.15**) during the study for various reasons, at least **838** subjects will be required to sign informed consent allowing to randomize **798** patients with **399** subjects per group (see cl. 1.8).

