### Secondary endpoints

1. Time to sustained clinical recovery from the new coronavirus infection COVID-19.
2. Proportion of patients hospitalized during 28 days of follow-up.

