### Additional endpoints

1. Time to COVID-19 progression to more severe level within 28-day follow-up period.

---

 **Severity of COVID-19** will be assessed in accordance with the criteria presented in the current 14th version dated 27.12.2021 Temporary Guidelines on Prevention, Diagnosis and Treatment of New Coronavirus Disease (COVID-19) (COVID-19)” of the Ministry of Health of the Russian Federation:

**Mild:** temperature < 38.0°C, cough, chest congestion, sore throat, nasal congestion/moderate rhinorrhea, cough, weakness, headache, muscle pain, nausea, vomiting, diarrhea, taste loss and olfaction loss, lack of laboured breathing/lack of dyspnea, SpO2≥95%, lack of criteria of moderate or severe form of the disease.

**Moderate:** body temperature >38.0°C; breathing rate >22/min; shortness of breath during exercise; CT (X-ray) changes, typical for viral lesions; SpO2 <95%; serum CRP >10 mg/L.

**Severe:** HR >30/min; SpO2 ≤93%; PaO2 /FiO2 ≤300 mm Hg; reduced consciousness; agitation; unstable hemodynamics (systolic BP < 90 mm Hg or diastolic BP < 60 mm Hg, diuresis < 20 mL/hour); lung changes on CT (X-ray), typical for viral changes; arterial blood lactate >2 mmol/L; qSOFA >2.

 **Stable clinical recovery** is determined as the first day of stable clinical improvement (at least 4 consecutive days, the improvement day is the first of the 4) to grade 1 or 0 (for rhinitis/nasal congestion, sore throat, weakness/fatigue, muscle pain/body ache, headache, chill, fever, nausea, diarrhea), to grade 0 (for dyspnea/laboured breathing and vomiting) to grade ≤ 2 (for cough) and lack of new symptoms grade 1 using 4-point scale (“Assessment of 14 Common COVID-19 Related Symptoms”, Appendix 1); in this case, the axillary temperature should be ≤37.3°C.

2. Proportions of patients with negative PCR test for SARS-CoV-2 on days 6 and 10 of observation.

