### **Study design**

Study design: multicenter, double blind, placebo-controlled, parallel group randomized clinical trial.

The study enrolls outpatients of either gender aged 18-75 years with increased body temperature  $> 37.5^{\circ}\text{C}$  and other symptoms of upper respiratory infection (cough, chest congestion, sore throat, nasal congestion/moderate rhinorrhea). The investigator should specify the patient's status of vaccination for COVID-19, influenza and other infections. Patients within the first four weeks after any vaccination/booster vaccination are not considered as candidates to participate in the study.

Nasopharyngeal swabs and rapid COVID-19 test are made after signing informed consent (two versions are used: 1) for patients consented for laboratory tests; 2) for patients without the consent). Patients with a positive rapid test and presence of mild COVID-19 (symptoms of upper respiratory infection, no symptoms of moderate or severe levels) within 24 hours after manifestation of the first symptoms of disease are considered as candidates for the study. Oxygen saturation (SpO2) is measured by pulse oximetry in all patients (pulse oximeters are provided by the study sponsor). If SpO2 is  $\geq 95\%$ , a patient may be selected for the study. Baseline severity of COVID-19 symptoms is evaluated using the scoring system «Assessing of 14 Common COVID-19-Related Symptoms» (FDA, 2020). This scoring system assesses the follows symptoms:

1. Stuffy or runny nose.
2. Sore throat.
3. Shortness of breath (difficulty breathing).
4. Cough.
5. Low energy or tiredness.
6. Muscle or body aches.
7. Headache.
8. Chills or shivering.
9. Feeling hot or feverish.

10. Nausea (feeling like you wanted to throw up).
11. Vomiting.
12. Diarrhea.
13. Sense of smell.
14. Sense of taste.

Each symptom is scored individually using the following scoring values:

- Items 1–10: None = 0; Mild = 1; Moderate = 2; and Severe = 3;
- Items 11 and 12: Not at all = 0; 1–2 times = 1; 3–4 times = 2; 5 or more times = 3;
- Items 13 and 14: Sense of smell/taste same as usual = 0; Sense of smell/taste less than usual = 1; No sense of smell/taste = 2.

The minimal baseline score for COVID-19-related symptoms is defined as follows: at least two symptoms with a score of 2 or higher, with the exception of taste and smell where subjects may have a score of 1 or higher, and the absence of shortness of breath (difficulty breathing).

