## **Inclusion and exclusion criteria**

### ***Inclusion criteria***

1. Male and female patients aged 18-75 years old.
2. Diagnosis of new coronavirus infection COVID-19 based on medical examination: axillary temperature  $>37.5^{\circ}\text{C}$ , symptoms of upper respiratory infection,  $\text{SpO}_2 \geq 95\%$ , no symptoms of moderate or severe levels.
3. The minimal baseline score for COVID-19-related symptoms defined as follows: at least two symptoms with a score of 2 or higher, with the exception of taste and smell where subjects may have a score of 1 or higher, and the absence of shortness of breath (difficulty breathing).
4. Positive rapid test for SARS-CoV-2 (COVID-19).
5. The first 24 hours from the disease onset.
6. Patients giving their consent to use reliable contraception during the study.
7. Signed patient information sheet (informed consent form).

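### No model or covariate is pre-specified for time to sustained clinical recovery, and the Visit 1 symptom score, already collected in every randomised patient, is left unused

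*Combined protocol and SAP*

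**What the plan says.** All references are to the combined protocol and SAP.

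- **Covariates.** In Evaluation of sample size, cl. 1.7, footnote 6 hangs on the words "primary endpoint" and states: "The analysis stipulates for obligatory assessment and accounting for effects of additional factors: history of vaccination and age/age groups of the subjects". Vaccination history and age are the only covariates the plan makes obligatory, and only for that endpoint.
- **The endpoint at issue.** "Time to sustained clinical recovery" is listed first under Secondary endpoints. No hypothesis, test, model or covariate is tied to it anywhere.
- **Its definition (footnote 2).** Nine symptoms must reach grade 0 or 1, shortness of breath and vomiting grade 0, and cough grade 2 or less. Axillary temperature must be no higher than 37.3°C and no new symptoms may appear. The state must last "at least 4 consecutive days, the improvement day is the first of the 4".
- **Entry (Inclusion criteria).** Patients need "at least two symptoms with a score of 2 or higher", with a lower bar for smell and taste. Shortness of breath must be absent, temperature above 37.5°C, and the time window is "The first 24 hours from the disease onset". No upper limit is set on the score.
- **Baseline data.** Under Study design, "Baseline severity of COVID-19 symptoms is evaluated using the scoring system" of 14 items, and the Schedule of study procedures places it at Visit 1.
- **Methods.** Non-parametric criteria lists LIFETEST and PHREG for survival analysis in general. Item 5 of Parametric criteria leaves the factor structure of models to fit statistics such as AIC.

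**The concern.** The first secondary endpoint has no fixed analysis. A log-rank comparison, a Cox model with treatment alone and a Cox model with any set of baseline factors would all be consistent with the text. These give different hazard ratios and different power, so the choice should be made before the treatment codes are known.

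The Visit 1 symptom score is the obvious candidate covariate. It is measured with the same instrument that defines recovery, before treatment, in everyone randomised. If it predicts recovery, leaving it out gives up power that would cost no extra patient, visit or assay.

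**Working it through.** **1. The plan's own sample size (primary endpoint).** Inputs from the SAS code in cl. 1.7: placebo rate 0.15, odds ratio 0.5, likelihood-ratio chi-square test, alpha 0.04, power 0.80.

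- Raphamin odds = 0.5 × 0.15/0.85 = 0.0882, so the rate = 0.0882/1.0882 = 0.0811.
- With f(p) = p ln p + (1 − p) ln(1 − p) and mean rate 0.1155, the noncentrality is √N × √{2[½f(0.15) + ½f(0.0811) − f(0.1155)]}. The smallest size reaching 80% is 356 per group (power 0.8001), which is the plan's 712.
- 712/(1 − 0.15) = 837.6, hence 838.

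Both figures reproduce. They concern the primary endpoint and do not depend on anything below.

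**2. Is the baseline score linked to recovery by definition?** Compare footnote 2 with the Inclusion criteria.

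- A patient entering with cough 2, smell 1 and 37.6°C already meets every symptom threshold and needs only a 0.3°C fall.
- A patient entering with eight symptoms at grade 3 must have all eight fall.
- Recovery thresholds exist for 9 + 2 + 1 = 12 of the 14 items. Smell and taste have none. Shortness of breath is absent in everyone at entry.

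The starting distance to the endpoint can therefore differ widely. That makes the score plausibly prognostic; it does not say how strongly.

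**3. What recovery effect could 712 patients detect?** The documents give no recovery effect. By Schoenfeld's formula at two-sided 0.05 and 80% power, HR = exp{2(1.960 + 0.842)/√D}:

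- D = 712 recoveries: exp(5.603/26.68) = 1.234
- D = 640: 1.248
- D = 500: 1.285

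At alpha 0.04, the value in the sizing code, D = 712 gives 1.242.

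**4. Power with and without the score.** Assumed throughout: 356 per arm, two-sided alpha 0.05, recovery in whole days and a standardised normal score. Row labels give the size of the log hazard ratio per SD, a higher score meaning slower recovery. The HR 1.234 runs used a Weibull time with shape 2 and median 8 days, censoring at Day 28 and 600 runs per setting. The HR 1.22 entries come from two separate sets, of 600 (a) and 400 (b) runs.

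| Log-HR per SD | Assumed HR | Unadjusted | Adjusted | Gain (points) |
|---|---|---|---|---|
| 0 | 1.234 | 77.8% | 77.5% | 0 |
| 0 | 1.22 (a and b) | 75% | 75% | 0 |
| 0.1 | 1.22 (a) | 72% | 73% | 1 |
| 0.2 | 1.234 | 75.8% | 79.0% | 3 |
| 0.2 | 1.22 (b) | 70% | 73% | 3 |
| 0.3 | 1.22 (a) | 69% | 72% | 3 |
| 0.3 | 1.22 (b) | 68% | 76% | 8 |
| 0.4 | 1.234 | 68.7% | 79.2% | 10 |
| 0.5 | 1.22 (a) | 59% | 73% | 14 |
| 0.5 | 1.22 (b) | 56% | 69% | 13 |
| 0.6 | 1.234 | 58.3% | 80.5% | 22 |
| 0.8 | 1.234 | 49.3% | 79.3% | 30 |

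Monte Carlo error is about 2 points on each power figure, which should be borne in mind when comparing the two 0.3 rows. On the log-hazard scale, values of 0.2, 0.4, 0.6 and 0.8 correspond to the score explaining 2%, 9%, 18% and 28% of the variation.

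**5. A limit of these runs.** Patients who progress or are hospitalised leave the study early (Study design), and this is not modelled. At the plan's rates, 356 × 0.15 + 356 × 0.0811 = 53.4 + 28.9 ≈ 82 of 712 patients (11.6%) would progress. If all left before recovering, at most about 630 recoveries would remain, slightly fewer than the D = 640 line in step 3.

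**The case against.** **The plan does not forbid adjustment.** A reader might infer that recovery will be compared without covariates. The documents do not say so: PHREG accepts covariates, Statistical criteria mentions checking proportional hazards, and the AIC rule could be read as letting the score in. The document also calls itself a protocol summary, so silence counts for less. This stands as to wording: the gap is missing pre-specification, not a stated unadjusted test. It does not close the gap. The AIC rule sits under Parametric criteria while PHREG sits under Non-parametric criteria, so read literally it does not reach this endpoint. If it did, the covariates would be chosen from the trial data.

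**The prognostic strength is unknown.** One might infer that baseline burden largely determines recovery time. Nothing in the documents supports that. Entry is limited to mild disease in the first day, two items have no recovery threshold, and cough at grade 2 already meets its own. This stands, and it is why the size is given as a range starting at zero.

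**The unadjusted hazard ratio is not biased.** At a log-HR of 0.5 per SD, a conditional 1.22 appears as about 1.18 without the score. That is non-collapsibility: the two ratios are different estimands. It argues for fixing the choice in advance, not for calling one of them wrong.

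**The primary endpoint.** It is tempting to ask also for Visit 1 temperature, SpO2 and concomitant disease in the primary model. Eligibility restricts the first two: temperature above 37.5°C with mild disease defined as below 38.0°C, and SpO2 of at least 95%. Simulated gains at 0.15 v 0.081 were nil at an odds ratio of 1.35 per SD, about 1 point at 1.65 to 2.0, and about 4 only at 2.7. That does not justify a change.

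**Conclusion.** The point holds as one of pre-specification and efficiency for the first secondary endpoint. Footnote 6 does not reach it, no model or covariate is named for it, and a baseline score closely tied to its definition is collected but unused.

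Under an assumed hazard ratio of 1.22 to 1.23 with 356 per arm, adjustment costs essentially no power when the score is uninformative. It gains about 3 points at a log-HR of 0.2 per SD, 3 to 10 at 0.3 to 0.4, and 13 to 22 at 0.5 to 0.6. The treatment effect, the recovery-time distribution and the prognostic strength are all assumptions, and early exit is ignored, so the direction is firmer than the size. Nothing here shows the planned inference to be invalid, and the 712 and 838 stand.

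**What to change.** Before unblinding, add to the SAP a Cox model for time to sustained clinical recovery with treatment, age, vaccination history and the Visit 1 symptom score as fixed covariates, not subject to selection by AIC. Preferably define the score as the sum of the 12 items that carry a recovery threshold. Keep the unadjusted comparison as a sensitivity analysis. Leave the primary endpoint's covariates as they are.

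The cost is SAP wording and a few lines of code; no new data, visits or patients are needed. The small downside is that the hazard ratio becomes a conditional one, so an unadjusted or standardised summary should be reported beside it.

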### ***Statistical criteria***

All the statistical calculations will be performed using two groups of statistical criteria:

- parametric – to obtain effective evaluations for parameters of random values, if the relevant conditions of applicability of methods/models are not violated (e.g. sphericity, normality, proportionality of risks, etc.);
- non-parametric – in any other cases.

### ***Parametric criteria***

The application of parametric criteria will be accompanied by a check of models for applicability (e.g. Kolmogorov-Smirnov test, Shapiro-Wilk test, etc.).

The following parametric tests and approaches are to be used:

1. To evaluate the differences of continuous variables obtained in one group at two different visits – Student's test for matched samples.
2. To evaluate the temporal dynamics of the compared indicators – analysis of variance (ANOVA) or covariance (ANCOVA) in the modification with repeated measures.
3. In case of multiple comparisons between the groups will apply a variety of corrections for multiplicity (Dunnett, Tukey, Scheffe, Holm adaptive test), etc.
4. In case of abnormal data distribution, approaches with the Generalized Linear Models and / or Mixed Linear Models will be used.
5. Selection of the type of distribution, specification of the factor and covariance structures of the model will be made using fit-statistics such as AIC (Akaike information criterion).

To perform the above-mentioned statistical tests and techniques, it is assumed that the following SAS procedures are used:

- 
- 1) Weekly epidemiological update: Omicron variant of concern (VOC) – week 2 (data as of 13 January 2022) EU/EEA <https://www.ecdc.europa.eu/en/news-events/weekly-epidemiological-update-omicron-variant-concern-voc-week-2-data-20-january-2022>

 This coefficient was complex: 5% patients will be screening failures.

 Akaike information criterion (AIC).

- UNIVARIATE – check for normality of the compared distributions;
- CORR, MEANS – calculation of descriptive statistics;
- TTEST – Student t-test with all the modifications;
- GLM – analysis of General Linear Models for studying temporal dynamics (ANOVA, ANCOVA);
- GENMOD – analysis of Generalized Linear Models;
- MIXED – analysis of Mixed Linear Models.

### ***Non-parametric criteria***

Below, there are the main types of possible comparisons with the respective criteria:

1. To evaluate the temporal dynamics of the compared indicators – Friedman test, nonparametric analogue of repeated measures analysis of variance.
2. For the frequency analysis of 2×2 cross tables –  $\chi^2$ -test (if the compared frequencies are greater than 5) or Fisher exact test (if one of the compared frequencies is less than 5).
3. For the frequency analysis of cross tables with independent strata – Cochran–Mantel–Haenszel test (modification of the  $\chi^2$ -test for multiple comparisons).
4. For the frequency analysis of data on the presence / absence of an event or outcome during repeated measures (cross tables with dependent strata) – survival analysis.

To perform the above-mentioned non-parametric statistical analysis options, it is assumed that the following SAS procedures are used:

- FREQ – Friedman test,  $\chi^2$ -test and / or Fisher exact test; Cochran–Mantel–Haenszel test
- LIFETEST, PHREG – survival analysis
- NPAR1WAY – Mann-Whitney U-test.

### ***Safety parameters***

Adverse events recorded during the study will be grouped into frequency tables by severity, seriousness and relationship with the study drug.

### ***Data presentation***

Descriptive statistics will be provided for each study continuous / interval variable. Numerical data will be presented by mean, standard deviation, min and max values (other measures of central tendency and variance may be provided where applicable). The data suggesting statistical conclusion will have the relevant confidence intervals. Extreme values (outliers) will be analyzed additionally. The data will be pooled according to visits. Categorical variables will be presented as per-visit frequency tables.

**Appendix 1 \***

**Table 1. Example of an Assessment of 14 Common COVID-19-Related Symptoms: Items and Response Options**

Example items
 
For items 1–10, sample item wording could be: “What was the severity of your [insert symptom] at its worst over the last 24 hours?”
	
Example response options and scoring†

1. Stuffy or runny nose	
None = 0
 
Mild = 1
 
Moderate = 2
 
Severe = 3

2. Sore throat	
3. Shortness of breath (difficulty breathing)	
4. Cough	
5. Low energy or tiredness	
6. Muscle or body aches	
7. Headache	
8. Chills or shivering	
9. Feeling hot or feverish	
10. Nausea (feeling like you wanted to throw up)	

11. How many times did you vomit (throw up) in the last 24 hours?**
	
I did not vomit at all = 0
 
1–2 times = 1
 
3–4 times = 2
 
5 or more times = 3

*continued*

*Table 1, continued*

12. How many times did you have diarrhea (loose or watery stools) in the last 24 hours?**
	
I did not have diarrhea at all = 0
 
1–2 times = 1
 
3–4 times = 2
 
5 or more times = 3

13. Rate your sense of smell in the last 24 hours
	
My sense of smell is THE SAME AS usual = 0
 
My sense of smell is LESS THAN usual = 1
 
I have NO sense of smell = 2

14. Rate your sense of taste in the last 24 hours
	
My sense of taste is THE SAME AS usual = 0
 
My sense of taste is LESS THAN usual = 1
 
I have NO sense of taste = 2

\* Note: Score values are included in the table for ease of reference. FDA cautions against including the score values within the response options presented to trial subjects to avoid confusing subjects.

\*\* The response options shown for items 11 and 12 are intended only for use with a 24-hour recall period.

\* Assessing COVID-19-Related Symptoms in Outpatient Adult and Adolescent Subjects in Clinical Trials of Drugs and Biological Products for COVID-19 Prevention or Treatment. FDA. Guidance for Industry. September 2020.
